and highlighting the need for more sensitive outcome measures in this group. Baseline (n=78) and 1 year (n=65) spirometry-controlled CT scans have been analysed and will be presented at ECFS and published shortly. Table 4 below summarises the PRAGMA scores analysed to date (unpublished). Table 3 outlines the key available data currently from the first phase of RECOVER showing significant improvements in all measured indices over 6 and 12 months. Over 6 months of ETI use, global CF Abd scores improved significantly from 15.0 \pm 1.4 to 10.7 \pm 1.1; p<0.0001, with significant improvements in sub-scores for domains of 'pain', 'GERD', 'impairment of quality of life' and 'appetite' but not 'disorders of bowel movement'.

	В	aseline (N	=114)		6 m (N=1	03) 12 m (N=90)		BL v all FU	BL v 6m	6m v 12m		
	N	Mean	Std Dev	N	Mean	Std Dev	N	Mean	Std Dev	p-value	p-value	p-value
Sweat Chloride	107	85.78	18.054	94	44.92	18.886	80	44.23	18.936	<.0001	<.0001	0.7358
LCI	82	12.21	3.829	83	10.14	3.689	49	9.85	4.274	<.0001	<.0001	0.3187
pp FEV1	114	83.65	15.399	82	91.73	16.032	87	92.11	16.319	<.0001	<.0001	0.7356
Weight z score	114	0.07	0.812	103	0.32	0.790	90	0.27	0.827	<.0001	<.0001	0.1253
BMI z score	114	0.12	0.819	103	0.36	0.792	90	0.28	0.863	<.0001	<.0001	0.0484
FeNO	112	13.59	10.407	103	16.30	12.397	90	15.96	12.397	0.0118	0.0192	0.7827
CFQR-RD	37	83.32	15.212	27	97.20	7.508	22	95.49	8.792	<.0001	<.0001	0.4386

 Table 3. Available cleaned data from people with CF aged 12 and over and one or more copies of

 F508del from the RECOVER study.

	All Participants						
	Baseline (N=85)			12 months (N=64)			Baseline v 12 mths
Variable	Ν	Mean	Std Error	Ν	Mean	Std Error	p-value
% Bronchiectasis	85	3.86	0.428	64	3.29	0.388	0.3256
% Disease	85	7.34	0.697	64	3.98	0.406	0.0001
% Trapped Air	85	20.61	1.606	63	11.48	1.749	0.0002
% Mucous plugging	85	2.22	0.351	64	0.11	0.042	<.0001
% Bronchial Wall Thickening	85	1.21	0.114	64	0.55	0.070	<.0001
	F508del/F508del						
	Baseline (N=55)			12 months (N=41)			Baseline v 12 mths
Variable	N	Mean	Std Error	N	Mean	Std Error	p-value
% Bronchiectasis	55	3.27	0.449	41	2.49	0.365	0.1769
% Disease	55	5.64	0.738	41	3.09	0.396	0.0030
% Trapped Air	55	13.90	1.790	41	9.01	1.666	0.0485
% Mucous plugging	55	1.35	0.335	41	0.07	0.033	0.0003
% Bronchial Wall Thickening	55	0.98	0.110	41	0.52	0.080	0.0010
	F508del/Minimum function						
	Baseline (N=30)			12 months (N=23)			Baseline v 12 mths

	(N=30)			(N=23)			v 12 mths

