The main foreseeable risk factor in this part of the study is the inability to collect a sputum specimen. Many patients, especially younger or healthier ones may not routinely produce sputum on a regular basis. We further suspect that, in light of the significant improvements in clinical outcomes demonstrated already for Kaftrio, that many individuals will go from being sputum producers to non-producers on treatment. We will work closely with the clinical teams to ensure that sputum specimens are optimized in terms of the split between laboratory and research processing. Each clinic has their own mechanism for trying to facilitate sputum production either at clinics or annual assessment – we will work with teams to ensure that saline induction, where used, can be facilitated by the research team to try to ensure a suitable sample sputum volume can be collected for all uses. We are aiming to collect 4 sputum samples over 2 years for RECOVER, with the baseline and year one samples prioritized. Where possible the research team will work with the subjects and clinical teams to ensure that all efforts are made to obtain a sufficient sample volume at these timepoints in particular, including sputum induction. The use of the TETRIS sputum processing protocol will mean that it is acceptable to use

P.I. [name] spontaneously produced and induced sputum interchangeably when obtaining samples. This will greatly facilitate optimal sampling.

We expect that an incomplete set of samples will be collected and have factored this into our study calculations in terms of numbers and budget. With a recruitment of 150 individuals to the advanced group we would ideally expect 600 sputum samples and 414 nasal lavage samples to process (1014 total). In reality we estimate that it is likely that we will have 90% of individuals produce one sputum sample, 80% to produce 2 samples, and 70% to produce 3 samples and 60% to produce 4 samples. We estimate that 80% of eligible individuals will produce one nasal lavage sample, 70% two samples and 60% three samples. The main foreseeable risk factor with nasal lavage is aspiration of isotonic saline. In practice this is a very similar procedure to sinus rinse which is commonly performed by many people with CF on a daily basis where we see almost no adverse effects in those who learn how to do the procedure. It is likely that some people may find this an uncomfortable or awkward procedure and elect not to do it.

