		comparisons using 7-21 subjects per group showed
		significant improvements in sweat chloride compared to
		controls

Table 12 Sample size examples in CF literature pertaining to RECOVER endpoints

Variable	Expected effect size	Mean	SD	Power (n=166)	Power (n=201)	Sample size for 90% power
CT scores	50% relative reduction in %disease at 2 years	2.62	2.59	62.0%	71.8%	325*
FeNO	100% increase in FeNO	8.5	5	>99%	>99%	39
GI inflammation	Reduction in stool Calprotectin by 50% (median [IQR]: 154.4 [102.1–284.2])	NA	NA	>99%	>99%	39
Abdominal scores	Reduction in CF Abd score by 5 points	19.9	5.6	89.2%	94.7%	169
CT scores	reduction by 20 points	71.2	17.3	>99%	>99%	65
Sweat chloride	reduction by 40 mmol/L	99.5	9	>99%	>99%	13
Nasal inflammation	Reduction of IL-8 by one third	1145	656	85%	92%	195

*See detailed discussion of this in Rosenow et al(105) who suggest a sample size requirement of 100 individuals to detect a 50% relative reduction in %disease at 2 years.

Table 13 Sample size calculations for RECOVER parent study where data is available

Treatment of Missing Data

To prevent loss of information and introducing potential selection biases, missing values may be imputed. Where patterns of missingness are not correlated with outcome variables, multiple imputation will be used under the missing at random assumption. Multiple imputation accounts for uncertainty in the standard errors, confidence intervals and p-values. Complete-case analyses will also be performed, and the results compared to the imputation results as a sensitivity analysis.

Descriptive Statistics

Descriptive statistics will be performed on all measured outcome variables and derived variables. A baseline table will present the demographic and clinical characteristics by treatment group and overall. Continuous variables will be summarized using means and standard deviations. Medians with interquartile ranges will be presented where appropriate. The distributions of continuous variables will be assessed to determine whether variable transformation may be required. Categorical variables will be summarised using counts and percentages.

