Statistical analysis of longitudinal data requires methods that can properly account for the intra-subject correlation of response measurement. Preliminary analysis of treatment group means over the time periods will inform more complex analyses of derived variables such as slopes, pre/post analysis and response trajectory over time. Linear mixed models will include demographic and co-morbidity covariates to adjust for confounders. Random effects will account for correlation among repeated measurements. Data transformation and distributional assumptions will depend on the types of data. A Normal distribution will be assumed for continuous variables. A Poisson distribution and log transformation will be assumed for count data. Categorical data will be analyzed using logistic or multinomial regression where appropriate. Model diagnostics will be applied to assess model fit, distributional assumptions and potential outliers. Where distributional assumptions are not met, non-parametric alternatives will be employed. Where there are multiple outcome measures relating to a specific aim, multiple comparison adjustments may be necessary. False discovery rate (FDR) adjustments will be applied where appropriate.

Biosample Collection, Processing and Storage Plan For Parent Study

Blood

Blood (15ml) will be collected, where possible, during clinically indicated venepuncture. And aliquoted as follows:

- 5ml in EDTA tube for DNA extraction. Sample transferred to the lab and frozen at -80°C for later transfer to Central labs and thereafter to our collaborators in Toronto (FR). This sample will be used for the CF Canada funded genetic modifier study.
- 10ml (or the remainder) will be transferred to a serum tube and transferred to the laboratory for processing. Samples will be centrifuged at 3000rpm and the supernatant (serum) aliquoted to 5 separate 1.5ml
 Eppendorf tubes. Aliquots will be labelled and frozen at -80°C. These aliquots to be sent to central labs and stored for future use.
- For the year 1 blood collection, 10ml blood will be collected and processed as above, frozen at -80°C, and sent to central labs.

Nasal Lavage

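### The trigger for multiple imputation is worded as a near missing-completely-at-random condition but labelled missing at random, so read literally it withholds imputation where missingness depends on observed outcomes

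*Protocol*

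**What the plan says.** Under Statistical Analysis, Treatment of Missing Data, the protocol makes three statements.

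- Purpose: "To prevent loss of information and introducing potential selection biases, missing values may be imputed".
- Trigger: "Where patterns of missingness are not correlated with outcome variables, multiple imputation will be used under the missing at random assumption".
- Role of complete cases: "Complete-case analyses will also be performed, and the results compared to the imputation results as a sensitivity analysis".

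The paragraph on longitudinal data later in the same chapter plans mixed models: "Linear mixed models will include demographic and co-morbidity covariates to adjust for confounders" and "Random effects will account for correlation among repeated measurements". It also allows pre/post analyses of derived variables, and non-parametric alternatives where distributional assumptions fail.

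Two other sections fix simpler methods. Airway Arginine/NO Metabolism assigns paired t-tests, Wilcoxon signed-rank tests or ANOVA to changes in the sputum laboratory outcomes. The Data Analysis part of Specific Aim 7 (parent study) assigns chi-squared, ANOVA and ANCOVA to adherence.

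Under Risks in Airway Inflammation data collection, the investigators expect that "many individuals will go from being sputum producers to non-producers on treatment", and they link this to clinical improvement.

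**The concern.** The condition and the label do not match. If missingness is unrelated to the outcomes, subjects with data are in effect a random subset as far as those outcomes go, and there is no selection bias to remove. Missing at random is the weaker assumption that missingness may depend on what has been observed, including a subject's earlier outcome values. That is where imputation corrects bias, and the literal trigger rules it out. This works against the purpose given in the sentence just before it.

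The condition is also a decision rule that someone must apply. Dependence on unseen values cannot be tested from the data. An analyst can only test whether missingness is associated with observed outcomes. Applied that way, the rule switches imputation off when an association is found, and the section says nothing about what to do then.

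What is at stake is any analysis that drops incomplete subjects. Its estimates would describe those who remained measurable rather than the cohort.

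**Working it through.** The protocol gives no figure to reproduce here, because the point concerns the wording of a rule. The check asks what each approach does under three missingness mechanisms.

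**Inputs from Table 3 (12+ cohort, LCI).** Baseline mean 12.21, SD 3.829 (n = 82). At 12 months, mean 9.85, SD 4.274 (n = 49). The difference in means, 9.85 - 12.21 = -2.36, is taken as the true change.

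**Assumptions (not in the protocol).** Bivariate normal values; baseline-to-12-month correlation r of 0.5, 0.7 or 0.85; about 60% of 12-month values kept; and, in the two non-random mechanisms, log-odds of being measured rising by 1 per SD of the driving variable. There were 1,000 simulated cohorts of 201. Imputation used baseline LCI only.

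**Formula for complete pairs when missingness depends on baseline.** The regression slope of the 12-month value on baseline is b = r × 4.274 / 3.829. The bias in mean change is (b - 1) × D, where D is the amount by which mean baseline in those measured exceeds the cohort mean. Under the assumed missingness, D is 0.335 SD, or 0.335 × 3.829 = 1.28 units.

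- r = 0.5: b = 0.558, bias = -0.442 × 1.28 = -0.57
- r = 0.7: b = 0.781, bias = -0.219 × 1.28 = -0.28
- r = 0.85: b = 0.949, bias = -0.051 × 1.28 = -0.07

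**Simulated bias in mean LCI change (true value -2.36).**

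| Mechanism | r | Complete pairs | Imputation under MAR |
|---|---|---|---|
| Completely random | 0.5 / 0.7 / 0.85 | 0.005 / -0.006 / -0.003 | 0.007 / -0.006 / -0.002 |
| Depends on observed baseline | 0.5 / 0.7 / 0.85 | -0.554 / -0.277 / -0.063 | 0.016 / 0.001 / 0.004 |
| Depends on unseen 12-month value | 0.5 / 0.7 / 0.85 | 0.781 / 0.549 / 0.343 | 1.116 / 0.807 / 0.449 |

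The simulated complete-pair results in the second row agree with the formula. Relative to 2.36 they are 23%, 12% and 3%.

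**Reading the table against the rule.** The trigger permits imputation in the first row, where it changes no bias. It excludes the second row, where imputation removes the bias. In the third row missing-at-random imputation is biased too, here more than complete pairs, so holding it back as the sole analysis is defensible there.

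**Which analyses are exposed.** A likelihood mixed model on all observed visits uses the baseline of a subject with no 12-month value. A paired t-test or signed-rank test on change does not, and ANOVA, ANCOVA or a pre/post difference also loses that subject unless values are imputed.

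**The case against.** There are four serious points on the other side.

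**Complete cases are not the stated fallback.** A reader might infer that outcome-related missingness is left to complete-case analysis. The text does not say so. It gives complete cases one role, a sensitivity comparison beside imputation, and leaves the outcome-related case unaddressed. This stands.

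**The mixed models already cover much of the ground.** Fitted by likelihood to all observed visits, they are valid under missing at random without imputation. In one check with assumed inputs (54% observed at 12 months, odds of measurement 1.5 to 2 times higher per baseline SD), complete cases overshot the true LCI change by 0.13 to 0.38, while a plain random-intercept model stayed within about 0.07. This stands for LCI and other repeated measures. It does not help the paired and ANOVA-type analyses.

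**The wording may be a loose statement of missing at random.** If the phrase means not dependent on unseen values, the rule is not reversed, and calling it fully inverted goes too far. That reading is possible, but it turns the condition into one that cannot be checked from data, so the sentence still needs rewording.

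**The evidence for outcome-related loss is limited.** A reader might take the LCI counts as proof: 82/114 (72%) at baseline, 83/103 (81%) at 6 months, 49/90 (54%) at 12 months. They are interim cleaned data collected during a pandemic. Completeness rose from baseline to 6 months, and baseline gaps cannot result from treatment response. The protocol attributes the main LCI risk to deviations in collection and timing. For sputum, loss that follows improvement is plausibly not at random, so missing-at-random imputation alone would not cure it. Both points stand.

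**Conclusion.** The point holds as a defect in a stated rule. The trigger is close to missing completely at random, carries the missing-at-random label, and, read literally, excludes the case in which imputation under that label removes bias. No method is stated for that case.

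The severity is moderate. For LCI the harm is small if the mixed models are fitted by likelihood to all observed visits. The exposure lies in the sputum metabolite tests, the adherence ANOVA/ANCOVA and any pre/post analysis.

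The 0.06 to 0.55 unit bias rests on assumed correlations, missingness strength and direction, and applies to a complete-pair analysis that the protocol does not make its main one. It shows that the wording can matter, not how far any result of this trial is off. The documents do not support a claim that the LCI estimates are biased by a known amount, or that LCI data are being lost because of outcome.

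**What to change.** Replace the trigger sentence with text such as:

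> Primary longitudinal analyses use likelihood-based mixed models on all observed visits. Where an analysis would drop incomplete subjects, multiple imputation is used under missing at random conditional on observed data, including earlier outcome values, age, genotype, site and ppFEV1. Complete-case analysis is a sensitivity analysis.

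ppFEV1 is a practical predictor because Table 3 has it for 87 of 90 subjects (97%) at 12 months.

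For sputum markers, add one not-at-random sensitivity analysis, such as a shift applied to imputed values or ranking non-producers as the best outcome, because the protocol expects loss to follow improvement. If a separate analysis plan already contains these elements, the protocol sentence should be aligned with it.

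The cost is two or three sentences and modest analysis time. No sample size, visit or data collection changes.

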We will undertake a detailed assessment of adherence as part of RECOVER so that we can link our findings in relation to treatment adherence to important disease outcomes. The treatment adherence arm of RECOVER will be led by [name], a clinical pharmacist at CHI Crumlin, who will undertake a five-year, part time PhD with RECOVER as the central theme. Prescribed medications at an individual level will be tracked throughout the study to ensure we have a reliable denominator on which to base adherence measures. A number of methods will be used in RECOVER to monitor and understand treatment adherence in the real-world setting:

- Electronic medication event tracking systems e.g. (MEMS®)
- Self-reported adherence
- Medication possession ratio (MPR) based on pharmacy pick up rates
- Qualitative assessment of beliefs and attitudes around adherence to ETI and other treatments

Medication Event Monitoring System (MEMS®)

This is the gold standard for electronic monitoring but can only measure monotherapy. It mimics a traditional pill bottle with the enhanced ability to track the date and time of each bottle opening.(92) Non adherence to MEMS® is less likely as the adherence pattern is recorded by the opening of the container for every dose. Therefore, it is used as a reference standard for validating other reference tools.(92) This data can be used to calculate the medication possession ratio per patient. Due to the high cost and additional support required this method of measuring adherence is under-utilized. We will measure adherence to ETI with MEMS® in a subset of RECOVER subjects in the Dublin Centres (approximately 100 individuals). MEMS® will not be used for adherence measurements with treatments other than ETI.

Parent/Subject Self-reporting of Adherence

This will be carried out using the up to date version of a specifically designed adherence scale for children and adults with CF(145) with the permission of the author [name] (a RECOVER collaborator). The treatment adherence questionnaire, barriers to adherence questionnaire and prescribed treatment plan will be used to monitor self-reported adherence.

Treatment Burden

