• What level of adherence with ETI is seen in the real world?

Measures of weekly adherence (using the three measures independently) will be reported and compared to previously published data on adherence rates with Ivacaftor(115, 147). Adherence over time, using all three methods, will be reported in a weekly fashion as treatment progresses. Changes in adherence over time (weekly, quarterly) will be assessed per individual and cross sectionally. We will explore the relationship between weight gain and subsequent adherence to ETI (because of concerns on behalf of some PWCF about excessive weight gain on modulators).

• Does adherence with other CF therapies decrease after ETI?

Adherence rates, using MPR and self-reported adherence, to medications individually and in groups (vitamins, mucolytics, nebulized antibiotics etc.) will be collected from 3 months prior to the introduction of ETI. The absolute change in adherence for 4 quarters (one before and three after) will be compared using chi squared and ANOVA. The rate of change of weekly adherence will be compared prior to and in the 9 months after (in 3 quarters) initiation of ETI using ANCOVA.

• Does poor adherence adversely affect outcomes?

This question will be addressed from the point of view of firstly, adherence with ETI, and secondly, adherence with other groups of medications. Medium term effects will be determined by comparing overall 12 and 24-month MPRs for given medications and groups of medications and specific relevant outcome measures such as CT scores, LCI, FEV1, nutritional status, antibiotic use and exacerbations at the end of 12 and 24 months respectively.

• Is adherence related to treatment burden?

Results from the various adherence measures will be compared, within individuals, to the CFQ-R treatment burden subscale results at each timepoint.

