Eligibility Assessment	Х	Х															
Sweat Chloride		Х				Х		Х				Х	Х	х	Х	х	Х
LCI	Х	Х				Х		Х		Х		Х	Х	Х	Х	Х	Х
Spirometry-controlled CT (A*)		Х						Х				Х		X1		X1	
Height/Weight/BMI*	Х	Х			Х	Х	Х	Х	Х	Х	Х	Х	Х	Х	Х	Х	Х
FEV1*	Х	Х			х	Х	Х	х	Х	Х	Х	Х	Х	х	х	Х	Х
Airway Sampling (Micro)*	Х	Х			Х	Х	Х	Х	Х	Х	Х	Х	Х	Х	Х	Х	Х
Nasal Lavage (A*)		Х				Х		Х				Х	Х	х	х	Х	Х
FeNO	Х	Х				Х		Х									
Liver Function Testing*		Х			Х	Х	Х	Х				Х	Х	х	Х	Х	Х
Liver Ultrasound		Х						Х				Х	Х	Х	Х	Х	Х
Sputum Collection (A*)		Х				Х		Х		Х		Х	Х	х	Х	Х	Х
Liver Examination		Х						Х				Х					
Stool Collection		Х	Х			Х						Х	Х	х	Х	Х	Х
Blood Collection		Х						Х				Х	Х	Х	Х	Х	Х
Breath Sample Collection		Х			Х	Х	Х	Х									
Abdominal Symptom Score	Х	Х	Х	Х		Х		Х				Х	Х	х	Х	Х	Х
CFQ-R		Х				Х		Х				Х	Х	Х	Х	Х	Х
Pharmacy Records MPR								Х				Х					
Adherence Questionnaire	Х	Х			Х	Х	Х	Х	Х	Х	Х	Х					
MEMs Caps Reading (M)								Х				Х					
Antibiotic Use		Х						Х				Х					
Adverse Event Check			Х	Х	Х	Х	Х	Х	Х	Х	Х	Х	Х	Х	Х	Х	Х
Mental Health Questionnaire													Х	Х	Х	Х	Х

* Collected as normal clinical care,

A - Advanced arm testing in RECOVER parent study

¹ Only for patients who performed spirometry-controlled CT in parent study. Scan at years four and six at sites doing routine clinical CT. Scan at year six for sites not performing biennial CT

M - MEMs study only

Table 14. Schedule of assessments. Each visit has a study window. For the RECOVER parent study the baseline visit (0 month visit) will have an 8 week pre commencement on ETI start window. The 1, 2 and 3 month visits have +/- 2 week window. The 6, 9, 12, 15, 18, 21 and 24 month visits have +/- 1 month window. For the RECOVER extension study each annual visit will have a window of +/- 4 month.

Study Governance and Management Plan

RECOVER

[figure not shown]

Figure 6 RECOVER study management structure.

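### MEMS caps are read only at months 12 and 24, with none at withdrawal, so participants who leave lose all electronic adherence data since their last reading

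*Protocol*

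**What the plan says.** The protocol's section on the Medication Event Monitoring System plans electronic monitoring of ETI, and of no other treatment, in a "subset of RECOVER subjects in the Dublin Centres (approximately 100 individuals". It treats the device as the reference method for electronic monitoring and says it can "track the date and time of each bottle opening".

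Under Specific Aim 7 for the parent study, Data Analysis, the first question is "What level of adherence with ETI is seen in the real world". The plan there is that "Measures of weekly adherence (using the three measures independently) will be reported", with comparison to published ivacaftor adherence, and that adherence over time by all three methods "will be reported in a weekly fashion as treatment progresses". The other two methods are self-report and "Medication possession ratio (MPR) based on pharmacy pick up rates".

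In Table 14 (Study Visit Timetable) the row "MEMs Caps Reading (M" has two marks, under months 12 and 24. The adherence questionnaire is marked at month -3, at baseline and every three months to month 24. The table has no early-termination column. The section on monitoring requirements asks that the date of and reason for withdrawal be available in source documents, but mentions no cap return. The section on drug interruption or discontinuation lets participants who stop ETI stay in the study.

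**The concern.** The cap stores a time-stamped history, so one reading recovers everything since it was issued. That works only if the cap comes back to be read. With readings twelve months apart and none tied to withdrawal, the record of someone who leaves is never retrieved if the schedule is followed as written. Leavers before month 12 contribute nothing, and leavers between months 12 and 24 contribute only their first year.

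The weekly curve is exposed at its start as well as its end. A person who leaves at month 8 used the cap in week 1, but that week is missing because the reading never took place. Week-1 adherence is therefore estimated only in people who stayed until a reading. If staying in the study goes with taking the drug, this selection raises the estimate and carries into the ivacaftor comparison. An analysis plan cannot repair it, because the data would never have been collected.

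**Working it through.** The protocol states no sample size, expected dropout or target precision for the MEMS component, so there is no figure to reproduce. The check has four steps.

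**1. Schedule.** Matching the row to the column heads of Table 14 puts the two marks under months 12 and 24. Data retrieved by time of leaving the study:

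| Leaves | MEMS data retrieved as scheduled |
|---|---|
| Before month 12 | None |
| Between months 12 and 24 | Up to month 12 |
| Completes month 24 | All |

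**2. Can another measure supply the weekly curve?** The possession ratio is calculated per 6-month period (section on Medication Possession Ratios), and questionnaires are three-monthly (Table 14). Only MEMS has dose-level time stamps, so weekly resolution depends on it. The Treatment Adherence background also says that self-report can overestimate adherence and that pick-up data give a maximum. It cites one ivacaftor study with 100% by self-report, 84% by possession ratio and 61% by MEMS.

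**3. Possible bias.** Let d be the share of cap users who leave before a reading, A_r the mean adherence of those read and A_l that of those lost.

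- True mean = (1 - d) × A_r + d × A_l
- Observed mean = A_r
- Overstatement = d × (A_r - A_l)

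For a given week, d is the share of those still in the study that week who leave before the next reading. It is largest just after a cap is issued or read and shrinks as the next reading approaches.

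Neither input is in the protocol, so both are assumed:

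- d = 5%, 10% or 21.1%. The last is 1 - 90/114, from the 12-month and baseline N in Table 3. The 6-month equivalent is 1 - 103/114 = 9.6%.
- Gap A_r - A_l = 0, 10, 20 or 40 points.

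Overstatement in percentage points:

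| d | Gap 0 | Gap 10 | Gap 20 | Gap 40 |
|---|---|---|---|---|
| 5% | 0 | 0.5 | 1.0 | 2.0 |
| 10% | 0 | 1.0 | 2.0 | 4.0 |
| 21.1% | 0 | 2.1 | 4.2 | 8.4 |

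With about 100 caps, these shares are about 5, 10 and 21 people.

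**4. How many leavers would have no MEMS data at all?** Assume a constant dropout rate giving a total D over 24 months. The share of leavers who go before month 12 is (1 - √(1 - D)) / D. For D = 10%, 20% and 30% this is 51%, 53% and 54%. About half of leavers would have no data, and the rest would keep year one.

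**The case against.** A reader might infer that everyone who leaves early gives no electronic data and that real-world ETI adherence will be overstated. The protocol does not support either statement in that form.

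- Someone who leaves at month 20 keeps a full year of MEMS data. Total loss applies only before month 12.
- Upward bias requires leavers to be less adherent. That is plausible, but no passage shows it, and people leave studies for other reasons. With no gap there is no bias.
- The 21% is not attrition. Table 3 is labelled as available cleaned data, and within it the N for percent predicted FEV1 rises from 82 at 6 months to 87 at 12 months, so the counts partly reflect data flow. They also describe the whole 12+ phase, not the Dublin MEMS subset.
- Stopping ETI is not leaving the study. Those who stop and stay can have the cap read at month 12 or 24.
- Self-report covers leavers to their last visit, and dispensing records do not depend on returning a device. Only the MEMS estimate is affected.
- The 61% comparator comes from 12 people. With an assumed SD of 20 to 30 points its standard error is 20/√12 = 5.8 to 30/√12 = 8.7 points, about as large as the worst case above.
- Nothing forbids an unscheduled reading, and a separate MEMS procedure might require cap return.

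All of this limits the size and reach of the point. The gap in the schedule remains: the protocol fixes the reading times, cites no procedure for leavers, and has no other measure fine enough for weekly reporting. The missing-data section reserves multiple imputation for missingness not correlated with outcome, which is doubtful when adherence data are lost because people leave.

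**Conclusion.** The point holds as a gap in a stated schedule. Followed as written, Table 14 leaves the MEMS record of leavers unretrieved since their last reading, so the weekly MEMS curve describes only those who reached one. The loss of data needs no assumption beyond some people leaving. Bias does: the direction is upward only if leavers are less adherent, and the size is 0 to about 8 points over the assumed ranges. The upper end combines the Table 3 proxy with the largest assumed gap, so it is a bound for illustration and not an expected value. The reach is the MEMS estimate in about 100 Dublin participants and its comparison with published ivacaftor adherence. The self-report and possession-ratio results stand apart. It is worth changing because the remedy is cheap and an unread cap may not be recoverable later.

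**What to change.** - Add to Table 14 a cap return and reading at withdrawal from the study.
- Add a download at the existing 6-monthly visits, or at the 3-monthly ones. A withdrawal reading does nothing for a person lost to follow-up who keeps the cap; interim downloads preserve the data up to the last visit at which the cap was read.
- State that weekly MEMS adherence is computed for everyone issued a cap, up to their last reading, and report for each period how many caps were issued, read and not recovered.

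No separate reading is needed when someone stops ETI but stays in the study, because the scheduled readings still apply.

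The cost is a few minutes per visit for about 100 participants and an arrangement for returning caps. More frequent downloads may make participants slightly more aware of being monitored, which favours the 6-monthly interval if that is a worry. Data after the last download of an unreturned cap would still be lost. The protocol describes the 6-11 phase as still recruiting, so the change may still save data there.
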